2.0 STUDY OBJECTIVES

2.1 Primary Objectives

2.1.1 To compare delirium incidence between recipients of high dose IV thiamine and placebo during hospitalization for allogeneic HSCT.

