3.0 Criteria for Evaluation / Study Endpoints

3.1 Primary Endpoint

Delirium incidence will be defined as: DRS > 12. Delirium rating scales will be performed at baseline (prior to transplant) and then three times weekly from day after transplant to 30 days after transplant or discharge, whichever comes first.

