7.5 Long-term Follow-Up Assessments

At one, three, and six months post-transplant the CRA(s) or investigators will meet with subjects to complete self-report assessments for depression (PROMIS-D), post-traumatic stress symptoms (PTSS-14), and HRQOL (FACT-BMT), as well as clinician-rated assessments of cognition (MOCA) and functional status (ECOG-PS). At the time of each follow-up, delirium assessments (DRS) will also be performed in participants who became delirious during the inpatient phase. Subjects will receive reminders regarding these long-term assessments via subjects' preferred method of contact. Long-term assessments will occur at one month (+/- two weeks), three months (+/- four weeks), and six months (+/- two months). The specified window at each of these follow-up time points will allow for assessments to coincide with BMT clinic visits. If a face to face assessment is not feasible, attempts will be made to perform assessments over the phone, through video conferencing, online, by email, or by mail. When assessments cannot be completed, this will be noted in the eCRF.

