7.11 Assessment of Efficacy

In order to be considered evaluable for efficacy, patients must:

- receive all 7 days of the treatment; a patient must receive at least 17/21 (80%) thiamine doses
- have delirium assessed at least weekly until one of the following is met:
 1. The participant is found to be delirious (DRS>12)
 2. The participant is at least 30 days post-transplant
 3. The participant is discharged

If a patient is deemed not evaluable, they will be replaced by a new patient. However, if a patient develops delirium during the intervention, they will still

receive the full 7 day course, not be replaced, and included in the efficacy analysis.

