9.3 Data Analysis Plans

To compare delirium incidence, severity, and duration between recipients of high dose IV thiamine and placebo during hospitalization for HSCT. The primary outcome measure is delirium incidence, defined as: DRS > 12. Secondary outcomes are differences in delirium duration (in days) and delirium severity, in which higher DRS scores suggest more severe delirium. A two group chi-squared test will be used to compare rates of delirium in the intervention and control group. Maximum severity score will be analyzed using two group t-tests, and time to delirium will be compared between groups using the Kaplan-Meier

method. For those with delirium, two group t-tests will compare the duration of delirium between intervention groups; Kaplan-Meier methods may also be considered for time to delirium resolution.

To determine if thiamine status is predictive of future delirium onset. We will examine the relationship between thiamine levels at the end of the seven day administration of thiamine and the development of delirium at any point during the thirty days post-transplant or the post-transplant hospitalization, whichever comes first. Patients who develop delirium prior to the end of the thiamine treatment will not be included in this analysis. We will examine the sensitivity and specificity of this relationship with ROC curves, and attempt to find a cutoff for thiamine levels that is associated with the development of delirium.

To investigate the effects of high dose IV thiamine on long-term health-related quality of life (HRQOL), functional status, depression, post-traumatic stress symptoms, and cognitive functioning in patients hospitalized for HSCT. Scores on FACT-BMT, PROMIS-D, PTSS-14, ECOG-PS and MOCA will be compared between intervention and control groups. We will summarize scores on the FACT-BMT, PROMIS-D, PTSS-14, ECOG-PS, and MOCA between the intervention and control groups at one, three, and six months post-transplant. Longitudinal modeling will be performed to examine differences/changes over time.

Safety Analyses: We will tabulate AEs and SAEs, by treatment and placebo, within strata. We will include all AEs which occurred at a rate of more than 5% in any treatment.

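### Time to delirium is planned by Kaplan-Meier with no rule for discharge or death, so the curve can exceed, and need not agree with, the crude in-hospital incidence

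*Combined protocol and SAP*

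**What the plan says.** The primary objective (2.1.1) is "To compare delirium incidence between recipients of high dose IV thiamine and placebo during hospitalization for allogeneic HSCT". Section 3.1 defines the event: "Delirium incidence will be defined as: DRS > 12". It schedules the scale "three times weekly from day after transplant to 30 days after transplant or discharge, whichever comes first". Section 9.3 analyses the endpoint as a crude proportion: "A two group chi-squared test will be used to compare rates of delirium in the intervention and control group".

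In the same paragraph, Section 9.3 adds that "time to delirium will be compared between groups using the Kaplan-Meier" method. That is all the plan says about this analysis. It states no censoring rule, no competing event and no test.

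Three other places bear on it:

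- Section 7.5: after discharge, "delirium assessments (DRS) will also be performed in participants who became delirious during the inpatient phase". Patients who left without delirium are not rated again, so a new onset after discharge cannot be recorded.
- Section 7.11: to be evaluable for efficacy, patients must "have delirium assessed at least weekly until one of the following is met". The three listed ends are delirium, day 30 and discharge. Death is not among them, and "If a patient is deemed not evaluable, they will be replaced by a new patient".
- Section 7.4: the scale is not done while a patient is unevaluable for an acute medical reason such as intubation or sedation.

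**The concern.** The objective concerns delirium in hospital. For that question, going home without delirium is a final outcome: the in-hospital event can no longer happen to that patient. Death without delirium is final in the same way. Standard Kaplan-Meier software, given a last-assessment date and no event, would censor these patients. Their later risk would then be represented by the patients still in hospital. One minus the curve at day 30 becomes the incidence in a hypothetical setting where nobody leaves, which is not the quantity in 2.1.1.

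At stake is the readability of the results. A curve reaching one figure at day 30, beside a crude proportion showing a lower one for the same patients and event, invites a reader to take the wrong number as the incidence. The plan does not say which rule it intends, so the choice would be made at analysis.

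**Working it through.** **1. The plan's own figure.** Inputs from Section 9.2: 0.445 against 0.155, 30 evaluable per arm, one-sided 0.05. The mean proportion is 0.30.

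- Standard error under the null: √(2 × 0.30 × 0.70 / 30) = 0.1183
- Standard error under the alternative: √((0.445 × 0.555 + 0.155 × 0.845) / 30) = 0.1122
- Power: Φ((0.29 − 1.645 × 0.1183) / 0.1122) = Φ(0.85) = 80.2%

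The stated 80% reproduces, and so does the odds ratio of 0.229. Nothing below changes this.

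**2. Direction.** Let λ be the daily delirium hazard and D the day of discharge.

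- In-hospital incidence to day 30: 1 − E[exp(−λ · min(D, 30))]
- 1-KM at day 30 with discharge censored: 1 − exp(−30λ)

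Since min(D, 30) never exceeds 30, the second is never below the first. They are equal only when no hazard remains after discharges begin.

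**3. Size, constant hazard.** The documents give no length of stay and no onset distribution, so D is assumed uniform and λ is solved to give the planned incidence. For discharge over days 14 to 30 the in-hospital incidence is

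1 − (e^(−14λ) − e^(−30λ)) / (16λ).

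At λ = 0.02712 this is 1 − (0.6841 − 0.4433) / 0.4339 = 0.445. Then 1-KM = 1 − e^(−0.8136) = 0.557. The other windows are solved in the same way:

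| Assumed discharge days | 44.5% appears as | 15.5% appears as |
|---|---|---|
| 14 to 30 | 55.7% | 20.6% |
| 17 to 35 | 50.5% | 18.1% |
| 20 to 40 | 47.5% | 16.8% |

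**4. Size, early onset.** With 80% of the 30-day hazard placed in days 1 to 14, the 44.5% appears as 48.1%, 46.5% and 45.6% for the same three windows. With 90% placed there it appears as 46.2%, 45.5% and 45.0%. With all of it there, the gap is zero.

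**5. A second model.** A day-by-day model with a constant daily discharge hazard, again on assumed timings, gave:

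| Delirium onset | Discharges begin | Would be released by day 30 | 1-KM for 44.5% | 1-KM for 15.5% |
|---|---|---|---|---|
| days 1-14 | day 14 or later | 50 to 95% | 44.5% | 15.5% |
| days 1-21 | day 18 | 80% | 45.6% | 16.0% |
| days 1-30 | day 18 | 80% | 52.6% | 19.1% |
| days 1-30 | day 14 | 80% | 56.2% | 20.7% |
| days 1-30 | day 14 | 95% | 61.4% | 23.6% |

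The last row is the most extreme setting tried. Death alone, at an assumed 5% or 10% by day 30, moves 44.5% to 45.5% or 46.5%, and 15.5% to 15.9% or 16.3%.

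**6. Effect on the comparison of arms.** In 2,000 simulated trials of 30 per arm under each of four settings, chi-squared power was 80 to 82% and log-rank power 81 to 83%, within one point of each other in every setting. The one-sided verdicts differed in 2 to 4% of trials. Control-arm 1-KM was never below the crude proportion. It was above it in 0%, 67%, 92% and 98% of trials, depending on the setting.

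**The case against.** The strongest reply is that the plan never says it will censor at discharge or death. Delirium-free patients who go home could be carried to day 30 as event-free, and the curve would then match the crude proportion. The incidence is also reported elsewhere, as a proportion with a chi-squared test. Kaplan-Meier is named only to compare arms, and time to delirium is not among the endpoints in 3.2 or 9.1. The between-arm test hardly changes. With 30 per arm, the 95% half-width around 44.5% is 1.96 × √(0.445 × 0.555 / 30) = 17.8 points, wider than any gap computed here.

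Most of this stands, and it rules out several stronger readings that a reader might infer:

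- *The curve will disagree with the primary endpoint.* It need not: the gap is zero if onsets precede discharges, and the censoring rule is itself an inference.
- *The primary result is biased.* It does not use Kaplan-Meier.
- *The next trial would be planned on inflated figures.* Section 9.2 ties effect sizes for a future study to the comparison of proportions and does not mention Kaplan-Meier estimates.
- *The figures show bias from healthier patients leaving first.* The calculation draws discharge independently of delirium risk. The gap is a difference in what is estimated, and the documents contain nothing from which to size informative discharge.
- *Death adds materially.* Patients who die before reaching 17 of 21 doses fail the evaluability rule and are replaced. How later deaths count is unclear.

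The sampling-error point does not remove the concern. Both figures come from the same patients and share that error, while the gap between them runs in one direction only. What remains is a planned analysis whose default form answers a different question from the objective, with no rule to prevent it.

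**Conclusion.** The point holds in a limited form. Section 9.3 leaves the handling of discharge and death open, although observation for new onset ends at discharge. Under the usual default, 1-KM can exceed the in-hospital incidence and cannot fall below it. With a constant hazard and uniform discharge over days 14 to 30, 44.5% would appear as about 56% and 15.5% as about 21%. With all onsets before discharges there is no gap. One harsher assumed discharge pattern reached 61.4% and 23.6%. All of these timings are assumptions.

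The effect is on how a supplementary curve is read. The primary chi-squared analysis, its power and the crude incidence are untouched, and the between-arm verdict changes little. A reader might also infer that the inflation will differ by arm through length of stay. That is possible, but the documents give no stay data to support or size it.

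**What to change.** In Section 9.3, replace the Kaplan-Meier sentence with four statements:

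1. Time to delirium is shown by arm as a cumulative incidence function (Aalen-Johansen) from the day after transplant to day 30. Discharge alive without delirium and death without delirium are competing events. When every patient is followed to delirium, discharge, death or day 30, the curve at day 30 equals the crude proportion.
2. The arms are compared by the log-rank test, described as a cause-specific comparison. Gray's test may be added but is optional.
3. In-hospital deaths are either in or out of the efficacy set, and the text says which, consistently with Section 7.11.
4. The text says how stretches without assessment (Section 7.4) are counted.

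The cost is a few sentences and a little extra analysis in standard software. Discharge and death dates must be confirmed as captured. Sections 5.7 and 7.11 imply that both are known, but the Time and Events table lists neither. No change to assessments, sample size or the primary analysis is needed.

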1.5 Rationale for Clinical Study

Delirium occurs in at least 40%, and up to 73%, of patients undergoing HSCT.^{10,11} Delirium is associated with longer length of stay,⁴ increased mortality,⁵ impaired activities of daily living,⁶ and can have profound immediate and long-term effects on mental health with studies demonstrating lasting symptoms of depression,⁷ post-traumatic stress,⁸ and impaired cognition.⁹

Thiamine deficiency is an underappreciated cause of delirium. Thiamine deficiency has been reported in 100% of patients undergoing HSCT.¹⁷ The co-occurrence of delirium and thiamine deficiency in HSCT is not known, but in cancer patients more broadly thiamine deficiency occurred in 55% of patients, 80% of whom demonstrated some mental status abnormality.¹⁶ There are not sufficient data to support a specific dosing strategy for thiamine repletion to target delirium due to thiamine deficiency in any patient population,²⁶ and no published studies investigating treatment or prophylaxis of delirium due to thiamine deficiency in HSCT patients.

In this double-blind, randomized controlled trial, we examine the use of high dose IV thiamine to prevent occurrence and decrease severity and duration of delirium. Our study design also allows for additional novel data on the temporal relationship between thiamine deficiency and delirium in HSCT patients.

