2.2 Secondary Objectives

2.2.1 To compare delirium severity between recipients of high dose IV thiamine and placebo during hospitalization for allogeneic HSCT.

2.2.2 To compare delirium duration between recipients of high dose IV thiamine and placebo during hospitalization for allogeneic HSCT.

2.2.3 To determine if thiamine status is predictive of subsequent delirium onset.

2.2.4 To investigate the effects of high dose IV thiamine on long-term health-related quality of life (HRQOL), functional status, depression, post-traumatic stress symptoms, and cognitive functioning in patients who undergo HSCT.

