7.3 Randomization

If the patient meets all inclusion/exclusion criteria, provides informed consent, and is not delirious ($DRS \leq 12$), the subjects will then be randomized in a 1:1 ratio to the intervention or control arms in a double-blind fashion such that the investigators, biostatistician, CRA(s), nursing staff, and subjects will not know which agent is being administered. The statistician of record will design a block randomization scheme, stratified by age (<65 or ≥ 65) and baseline cognitive function ($MOCA >25$ or ≤ 25), both well-known risk factors for delirium. This information will be provided to UNC Investigational Drug Services, who will manage the actual assignment of subjects to each arm using the randomization list designed by the statistician.

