9.2 Sample Size, Accrual and Duration of Accrual

For the primary objective of comparing delirium incidence between groups, a two group chi-squared test with a 0.050 one-sided significance level will have 80% power to detect the difference between a usual care proportion of 0.445 and an intervention proportion of 0.155 (odds ratio of 0.229) when the evaluable sample size in each group is 30. The anticipated rate of delirium in the control group is based on 43 – 73% incidence of delirium during hospitalization for HSCT reported in the literature. As this is the first study to evaluate the efficacy of thiamine as a prevention strategy for delirium, no data is available to generate an estimate of delirium incidence in the intervention group. However, the odds ratio (OR) hypothesized for this study is in line with other successful delirium prevention trials.^{42,43} Even if the delirium incidence in the IV thiamine group is not this low, the results of this study will provide effect sizes and 95% confidence intervals to power a future larger study.

Our sample will include 60 adult participants. UNC tumor registry records demonstrate that between 2015 and 2016 133 patients were admitted for allogeneic stem cell transplant. We estimate that we will enroll at least 50% of eligible patients, based on recruitment rates described in previous delirium intervention studies,⁴⁴ allowing us to recruit our target of 60 evaluable participants in approximately two years and complete our study in the proposed three year grant period.

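### Delirium duration is compared only in patients who became delirious, so the arm difference is biased if thiamine prevents episodes that are longer or shorter than those that remain

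*Combined protocol and SAP*

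**What the plan says.** Secondary objective 2.2.2 is stated for recipients of each treatment, not for delirious recipients: "To compare delirium duration between recipients of high dose IV thiamine and placebo during hospitalization for allogeneic HSCT". Section 3.2.1 measures duration in days and gives no value for a patient who never becomes delirious.

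Section 9.3 then narrows the analysis: "For those with delirium, two group t-tests will compare the duration of delirium between intervention groups". The alternative it mentions is optional: "Kaplan-Meier methods may also be considered for time to delirium resolution". Maximum severity, in the same section, carries no such restriction as written: "Maximum severity score will be analyzed using two group t-tests".

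Two other places set the context. Under 7.3, a patient is randomised only if he or she "provides informed consent, and is not delirious" (DRS of 12 or below). Section 9.2 sizes the trial to detect a difference between "a usual care proportion of 0.445 and an intervention proportion of 0.155", with 30 evaluable patients per arm. No section plans a duration analysis in all patients or labels the cases-only comparison descriptive.

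**The concern.** Because everyone starts free of delirium, membership of the analysed group is decided after randomisation, by the event the treatment is supposed to prevent. Randomisation balances the arms as a whole; it does not balance the patients who go on to have an episode. Suppose thiamine prevents mainly short episodes. The thiamine cases that remain are then the long ones, and thiamine appears to prolong delirium. If it prevents mainly long ones, it appears to shorten the rest. Either result can arise when thiamine changes the length of no remaining episode.

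The Kaplan-Meier option can deal with episodes still open at the end of observation, but it starts from the same selected patients and so leaves this problem in place.

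What is at stake is the reading of one named secondary objective. A mean difference or p-value from this test would be taken as the effect of thiamine on duration, when it may reflect only which episodes were prevented.

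**Working it through.** **1. The plan's own figure.** Inputs from 9.2: p1 = 0.445, p2 = 0.155, n = 30 per arm, one-sided alpha 0.05; mean proportion 0.30.

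Power = Φ{[0.29·√30 − 1.645·√(2·0.30·0.70)] / √(0.445·0.555 + 0.155·0.845)} = Φ{(1.588 − 1.066)/0.615} = Φ(0.85) = 0.802. The stated 80% is reproduced. The plan gives no corresponding figure for duration.

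**2. Who enters the duration test.** 30 × 0.445 = 13.35 placebo and 30 × 0.155 = 4.65 thiamine patients. For Binomial(30, 0.155), P(3 or fewer) = 0.295 and P(0 or 1) = 0.042. If thiamine incidence were 0.30 (assumed), 30 × 0.30 = 9 thiamine patients would enter.

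**3. When the difference is biased.** Assume thiamine causes no delirium and alters no remaining episode. The share of placebo-type episodes missing from the thiamine sample is s = (0.445 − 0.155)/0.445 = 0.652, and

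bias = s × (mean length of unprevented episodes − mean length of prevented episodes).

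This is zero if s = 0 (incidence unchanged) or if the two means are equal. Otherwise its sign follows the bracket, on which the documents give no information.

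**4. An illustrative size.** Assumptions not supplied by the documents: exponential episodes with mean 5 days; r is the latent-scale correlation between an episode's length and its chance of persisting on thiamine. Simulated mean days on thiamine (placebo 5.0):

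| Thiamine incidence | r = -0.35 | -0.10 | 0 | 0.10 | 0.35 |
|---|---|---|---|---|---|
| 0.155 | 3.4 | 4.5 | 5.0 | 5.5 | 6.7 |
| 0.30 | 4.1 | 4.8 | 5.0 | 5.2 | 5.8 |

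At 0.445 (no effect on incidence) the mean was 5.0 at r = -0.35, 0 and 0.35. The unrounded extremes at 0.155 are 3.40 and, over repeat runs, 6.74 to 6.75, so the bias runs from about 3.40 − 5 = -1.6 to 6.75 − 5 = +1.75 days.

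**5. Set against the noise.** The 95% CI half-width for the mean difference is t(0.975, n1+n2−2) × √(1/n1 + 1/n2) SD: 1.12 SD at 13 vs 5, 0.90 at 13 vs 9, 0.81 at 13 vs 13. With an SD of 5 days (exponential, mean 5), 1.116 × 5 = 5.6 days at 13 vs 5.

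**6. Error rate.** For |r| up to 0.35, a two-sided 0.05 t-test is significant in 3.7 to 11.4% of simulated trials at 0.155, 4.1 to 6.5% at 0.30 and 4.2 to 4.5% at 0.445. The level is assumed, since 9.3 gives none for duration. One-sided at 0.05, a false finding of shorter delirium reaches 8.9% at r = -0.35.

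**7. The all-patient comparison.** Counting 0 for those never delirious, mean days per patient on placebo are 0.445 × 5 = 2.23. On thiamine at 0.155 they are 0.53, 0.78 and 1.05 for r = -0.35, 0 and 0.35, giving differences of -1.70, -1.45 and -1.18. The sign no longer depends on which episodes were prevented.

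**The case against.** **Episode length is a legitimate question.** Section 1.5 speaks of using thiamine "to prevent occurrence and decrease severity and duration of delirium", which can be read as shorter episodes in those who have them. An all-patient total answers a different question, total burden, and partly repeats the incidence result. This stands: it is a reason to keep the cases-only estimate, but not to present it as a randomised comparison.

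**The planned test is better in one setting.** If incidence is unchanged and every episode is halved, the cases-only t-test is unbiased and detects the change in 32 to 34% of simulated trials, against about 22 to 23% for a permutation test of all-patient mean days. This also stands and should be disclosed.

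**The bias is small beside the noise, and the endpoint is secondary.** Correct under the assumptions in step 4. Section 8.5 describes the trial as gathering preliminary data.

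Three stronger readings are tempting, and the documents do not support them:

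- A reader might infer that the duration comparison is necessarily biased. Step 3 shows that it needs both a change in incidence and a link between prevention and length.
- A reader might infer that the bias is large. Starker assumed contrasts do give more: unprevented episodes averaging 6 days and prevented ones 2 give 0.652 × 4 = +2.61 days and a false finding of longer delirium in 29% of trials. The documents contain no episode lengths, so nothing in them supports such a contrast.
- A reader might infer that a distorted duration effect will be used to size the next trial, because 9.2 says "the results of this study will provide effect sizes and 95% confidence intervals to power a future larger study". That paragraph opens with the primary objective and the sentence itself concerns delirium incidence, so its natural reading is incidence effect sizes.

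**Conclusion.** The concern holds in conditional form. The planned duration test compares groups selected after randomisation, and no other analysis in the plan makes up for it. Whether the result is biased, and in which direction, depends on which episodes thiamine prevents, and the documents do not say. At the planned incidences, with exponential 5-day episodes and |r| up to 0.35 (all assumed except the incidences), the bias is about -1.6 to +1.75 days, inside a CI half-width of roughly 5.6 days. The risk lies more in how the estimate is read than in the error rate. The primary incidence test is unaffected. This is a cheap improvement of modest importance.

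**What to change.** Amend the duration paragraph of 9.3 as follows.

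1. **Keep the cases-only estimate with its CI**, as time to resolution with episodes still open at discharge or day 30 censored. Label it descriptive and state that it is not a randomised comparison.
2. **Add the between-arm comparison**: total delirium days through day 30 or discharge in all randomised patients with post-transplant DRS data, with 0 for those never delirious. Report the difference in mean days with a 95% CI and a test of that same quantity, for example a permutation test of mean days stratified by the randomisation factors in 7.3 (age and MOCA).
3. **Do not pair the mean difference with a rank test.** In simulation at 0.445 vs 0.155, a rank test was significant in 70% of trials and a Welch test of the mean in 41%, disagreeing in 31%. With episodes halved at equal incidence, the rank test detects the change in only about 8%.
4. **Report by arm** how many randomised patients lack DRS data, since having data is itself settled after randomisation. Give the efficacy-evaluable population of 9.1 as a supporting analysis.

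The cost is SAP wording. Section 5.7 already keeps patients in follow-up after they stop treatment. Patients replaced under 7.11 must stay in the data set, although those replaced for missed weekly DRS will have gaps. How to count deaths and days without a DRS (3.2.1, 7.4) is a separate detail to settle in advance.

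State the downsides in the plan. The new measure is total burden and is driven partly by incidence, so it is not independent evidence of shorter episodes. It depends on length of stay, because counting stops at discharge. It has less power than the cases-only test if only episode length changes.
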